2.3 RISK/BENEFIT ASSESSMENT

2.3.1 KNOWN POTENTIAL RISKS

Study participants will not have any increased risk or cost for participating in this study. Participants in the study have the same risks as those undergoing corneal transplantation in other settings. Many of the risks in this study are inherent risks of corneal transplantation; thus, there is no known increased risk associated with participation in this study.

As with any surgery, there are risks associated with these surgeries, and both surgeries have similar risks. There is a risk of infection or bleeding which could result in vision loss. There may be damage to the tissue graft during tissue preparation, and the tissue graft can fail to attach to the cornea; thus, there may be a need for repeat air injection.

Below, the other risks associated with each type of surgery are listed:

- UT-DSAEK: There may be slightly decreased vision after surgery compared to DMEK, although this is unknown. The healing process may also be slower. Some think there is an increased risk of rejection compared to DMEK, although this is also unknown. There is a small risk of intraocular pressure rise with painful glaucoma attack in the immediate postoperative period that can cause permanent glaucomatous optic nerve damage resulting in visual field deficits.
- DMEK: There may be increased risk of tissue loss, repeat air injection, detachment of the tissue graft to the cornea compared with UT-DSAEK. There may be higher costs associated with this surgery, although these additional costs will be covered by insurance. There is a small risk of intraocular pressure rise with painful glaucoma attack in the immediate postoperative period that can cause permanent glaucomatous optic nerve damage resulting in visual field deficits.
- DSO: The healing process may be slower than after DMEK or UT-DSAEK. There is a risk that a second surgical for endothelial keratoplasty would be required. Topical ripasudil may cause a local allergic reaction, eye redness or irritation, or upset stomach.

Blindness due to infection may occur in extremely rare cases. There may also be differences in rates of difficulty with donor preparation, increased intra-operative times, graft rejection and graft survival, and donor attachment in DMEK versus UT-DSAEK. Even if there is a total detachment during DMEK, we will continue to move forward with secondary treatment. These risks will be addressed by the enrollment site by making sure all protocols are being followed thoroughly and by following up with participants after surgery.

DETECT

Version 5.0
21 March 2023

There are no known risks directly related to the Endoserter, jones tube, or cannulas. There may be some discomfort during follow-up testing (BSCVA, IOP, slit lamp, Pachymetry, Pentacam, endothelial imaging and OCT testing and photo imaging inside the eye), but this will be kept to a minimum. The participant will be asked to tell the doctor if any of this testing feels painful.

Anesthesiology will be determined as per the participants needs. They will generally be awake with medications given to help them relax and feel comfortable. This is called monitored anesthesia care. Other participants may require general anesthesia care. While this is generally safe, there are small increased risks to the heart and lungs which will be discussed with the anesthesiologist. Both types of anesthesia are routinely used for DMEK and DSAEK surgeries, although generally monitored anesthesia care is the typical route.

The most commonly reported adverse effects of topical ripasudil 0.4% include irritation, blepharitis, honeycomb edema, conjunctival congestion, conjunctival hyperemia, and conjunctival inflammation. Other risks include conjunctival hyperemia, guttata-like bodies with reversible morphologic changes.

2.3.2 KNOWN POTENTIAL BENEFITS

Corneal transplantation is among the most commonly performed transplant surgeries in the world, and endothelial keratoplasty is the most common type of corneal transplantation. There is reasonable evidence that our interventions (DMEK and ripasudil) will improve outcomes for those undergoing endothelial keratoplasty. If our hypotheses are correct, there could potentially be a profound societal benefit for future patients.

2.3.3 ASSESSMENT OF POTENTIAL RISKS AND BENEFITS

Knowledge gained from this study may help improve outcomes for patients undergoing endothelial keratoplasty, and may prolong the lifespan of transplanted tissue. Given the minimal risks to participants in this study, we feel the benefits of the important knowledge we expect to gain from this study outweigh the risks.

3 OBJECTIVES AND ENDPOINTS

OBJECTIVES	ENDPOINTS	JUSTIFICATION FOR ENDPOINTS
Primary		
Specific Aim 1: To determine whether DMEK has superior post-operative best-spectacle corrected visual acuity (BSCVA) compared to UT-DSAEK and DSO	BSCVA at 12 months	The most clinically important outcome for patients
Specific Aim 2: To determine if rho-kinase inhibitors affect endothelial cell loss in patients undergoing endothelial keratoplasty	Endothelial cell density at 12 months	Endothelial cell loss corresponds with risk of subsequent graft failure
Secondary		
Specific Aim 1: To determine whether DMEK has superior post-operative BSCVA compared to UT-DSAEK and DSO	BSCVA at 3, 6, and 24 months	The most clinically important outcome for patients
Specific Aim 2: To assess the effect of surgery type on endothelial cell loss	Endothelial cell loss at 3, 6, 12, 24 months	Endothelial cell loss corresponds with risk of subsequent graft failure

DETECT

Version 5.0
21 March 2023

OBJECTIVES	ENDPOINTS	JUSTIFICATION FOR ENDPOINTS
Specific Aim 1: To assess the safety profile of each surgery type	Complications over the course of the entire study period, including re-bubble rate, graft rejection, and primary graft failure	Complications rates are important to consider when deciding on a surgery type
Specific Aim 2: To determine if rho-kinase inhibitors affect endothelial cell loss in patients undergoing endothelial keratoplasty	Endothelial cell density at 3, 6, and 24 months	Endothelial cell loss corresponds with risk of subsequent graft failure
To determine the effect of study interventions on quality of life	National Eye Institute Visual Function Questionnaire (VFQ) post-operatively at 3 months and 12 months as compared to baseline	Quality of life is an important patient outcome and will help determine if any differences in BSCVA or endothelial cell density are clinically relevant. The previous DETECT-TES found DMEK to have significantly better visual acuity outcomes but no difference in VFQ
To determine the effect of study interventions on adverse events	Adverse events over entire study period	To ensure safety of the interventions
To assess the relative role of light scatter on visual acuity	Pentacam densitometry at baseline and post-operatively at 3, 6, 12, 24 months	Correlates with clinical outcomes, and may provide a sensitive surrogate endpoint for future clinical trials
To assess the relative role of higher-order aberrations on visual acuity	Pentacam HOA at baseline and post-operatively at 3, 6, 12, 24 months	Correlates with clinical outcomes, and may provide a sensitive surrogate endpoint for future clinical trials
To assess the effect of ripasudil on graft thickness	An RCT comparison of graft thickness as measured by pachymetry on donor tissue post-operatively at 6 and 12 months controlling for baseline	Objective measure of the effect of ripasudil on graft function
To assess the relative role of graft thickness on visual acuity	Graft thickness as measured by pachymetry on donor tissue pre-operatively and post-operatively at 3, 6, 12, 24 months	Important to understand how graft thickness affects visual acuity to guide future surgeries
To assess the cost-effectiveness of each intervention	Cost-effectiveness analysis at 24 months	Important factor to consider when recommending surgery
To assess the effect of surgery type on refractive outcomes	Manifest refraction at baseline and post-operatively at 3, 6, 12, 24 months	Important to assess the relationship between surgery and refraction

DETECT

Version 5.0
21 March 2023

4 STUDY DESIGN

4.1 OVERALL DESIGN

DETECT I

Descemet Endothelial Thickness Comparison Trial (DETECT) I is a multi-center, outcome-masked, placebo-controlled clinical trial randomizing 160 patients in a 2x2 factorial design. The purpose of this study is to determine differences in visual outcomes between two types of corneal transplant surgeries, ultrathin Descemet stripping automated endothelial keratoplasty (UT-DSAEK) and Descemet membrane endothelial keratoplasty, and to determine the effect of rho-kinase inhibitors on endothelial cell loss in patients with moderate Fuchs endothelial dystrophy, bullous keratopathy, prior graft failure, controlled uveitis or controlled glaucoma. Patients presenting to Oregon Health & Science University, Stanford University, University of Pennsylvania, University of California Davis, or to Dartmouth-Hitchcock Medical Center with isolated endothelial dysfunction who are good candidates for both types of endothelial keratoplasty performed in this study will be eligible for inclusion. Participants will be randomized to one of four treatment groups in this 2x2 factorial design study:

- 1) UT-DSAEK plus topical ripasudil 0.4%
- 2) UT-DSAEK plus topical placebo
- 3) DMEK plus topical ripasudil 0.4%
- 4) DMEK plus topical placebo

We hypothesize that DMEK will result in improved visual acuity at all time points compared to UT-DSAEK. We anticipate that DMEK will have higher ECL than UT-DSAEK. We hypothesize that endothelial cell loss at 12 months will be lessened in those receiving rho-kinase inhibitors, after controlling for pre-operative endothelial cell density.

DETECT II

Descemet Endothelial Thickness Comparison Trial (DETECT) II is a multi-center, outcome -masked trial randomizing 60 patients with Mild Fuchs endothelial dystrophy to DMEK versus DSO with adjunctive Ripasudil. The purpose of this study is to determine visual outcomes between these two surgical interventions. Participants will be randomized 1:1 to one of two treatment groups:

- 5) DMEK plus topical placebo
- 6) DSO plus topical ripasudil 0.4%

We anticipate that DMEK will result in improved visual acuity at all time points compared to DSO. We hypothesize that DMEK will have higher ECD at 12 months that DSO.

All study participants will be masked to their intervention. The refractionist performing the BSCVA will also be masked. Due to the nature of the intervention, the surgeon and technician performing study visit endothelial cell density and other imaging will not be masked as to surgery type (but will be masked as to study medication); however, the image graders at the Proctor Reading Center and CIARC will be masked. All study medications and placebo will be labelled identically to ensure adequate masking of study physicians and patients. An interim analysis will be performed once primary outcome data is available for one half of the patients (see **Section 9.4.6** of this protocol for details). The enrollment period is 24 months.

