Study participants will all undergo either DMEK + topical placebo or DSO + ripasudil. All patients will be randomized to undergo one of these two surgical interventions. All patients randomized to DSO will receive topical ripasudil 0.4% post-operatively and all patients randomized to DMEK will receive topical placebo. Patients will begin topical medicines post-op day 1. They will take their assigned study medication 4x/day for 3 months.

Study Duration: 5 years
Participant Duration: 24 months

DETECT

Version 5.0
21 March 2023

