4.3 JUSTIFICATION FOR DOSE

Route of administration and dosage of topical ripasudil 0.4% are consistent with previous studies of the drug. Topical placebo will be administered in the same way as topical ripasudil to mask the patient, physician, and study staff. The topical placebo solution will have the same clear appearance as ripasudil to maintain masking.

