6.2.7 STUDY MEDICATION DISTRIBUTION

Once the study drug has been prepared, it will be released to the shipping department where it will be shipped directly to the patient. Validated shipping methods per storage conditions and temperature requirements will be ensured during shipment. Medications and masked placebos will be provided to each patient individually from the partner pharmacy.

In addition to ripasudil/placebo, DETECT II patients will receive a second study medication. Initially all DETECT II patients will receive dexamethasone. The enrolling physician will prescribe 10mL of dexamethasone eye drops to begin post-operatively. After 30 days, partner pharmacies will provide the second study medication. Those randomized to DSO will switch to a placebo and those randomized to DMEK will continue on dexamethasone. Medications and masked placebos will be purchased by the study and distributed to each enrolled patient individually by the partner pharmacies.

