6.3 MEASURES TO MINIMIZE BIAS: RANDOMIZATION AND BLINDING

For both trials, patients will be randomized by the eye bank 1-3 weeks prior to surgery. In DETECT I, each study eye will be randomly assigned separately to the two treatment groups (DMEK/UT-DSAEK, ripasudil/placebo). Block randomization will be performed using a computer program (Statistical package R; Version 3.6; R Foundation for Statistical Computing, Vienna Austria) by the data coordinating center. Once an eye is enrolled in the study, the study coordinator will assign the study participant's eye an ID (alpha-numeric code).

Prior to surgery, the eye bank will assign the study participant corneal tissue. Once the corneal tissue has been assigned, the eye bank will look at the treatment assignment with regard to surgical treatment and prepare the tissue accordingly. For DETECT II, the tissue will be randomized and assigned to the patient if the patient is randomized to DMEK. The eye bank will also inform the surgeon of the study participant's randomization assignment with regard to type of surgery.

The eye bank will randomize tissue using the Microsoft Excel RANDBETWEEN formula. A new file will be created for each study eye and uploaded to REDCap. The eye bank will highlight the randomized tissue in the Excel file (the randomization runs every time the file is opened), so the original randomization is documented. If tissue does not pass post-processing evaluation, becomes ineligible for some other reason, or it does not meet study parameters, e.g. >90 microns, the randomization process will be repeated, the same Excel file can be used.

Once the study eye has been assigned a study participant ID and randomized to treatment group they will be included in the intention to treat analysis. (Note: See **MOP – Section 4.3** for full donor tissue procurement and assignment information).

All study participants will be masked to their intervention. The refractionist performing the BSCVA will also be masked. Due to the nature of the intervention, the surgeon and technician performing study visit endothelial cell counts and

DETECT

Version 5.0
21 March 2023

other imaging will not be masked as to surgery type (but will be masked as to study medication); however, image graders at the Proctor Reading Center and CIARC will be masked. Eye bank personnel will not be given any identifying information.

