6.5.1 RESCUE MEDICINE

The masked treating physician will be allowed to add or change any therapy deemed necessary, including surgery. These changes will be recorded and reported.

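### In DETECT II the operation determines the study drug and the later steroid bottle, so the stated masking of surgeon and imaging technician to study medication cannot hold there

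*Protocol*

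**What the plan says.** **The masking claim.** Section 4.1 describes both trials and then gives one masking paragraph. The surgeon and the technician who takes the endothelial and other images "will not be masked as to surgery type (but will be masked as to study medication". Section 6.3, which opens by addressing both trials, repeats it: those doing endothelial counts and "other imaging will not be masked as to surgery type (but will be masked as to study medication". Section 4.1 adds: "All study medications and placebo will be labelled identically to ensure adequate masking of study physicians and patients". Section 4.3 gives the placebo the same purpose: "Topical placebo will be administered in the same way as topical ripasudil to mask the patient, physician, and study staff".

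**The DETECT II arms.** The synopsis fixes the drug by operation: "All patients randomized to DSO will receive topical ripasudil 0.4% post-operatively and all patients randomized to DMEK will receive topical placebo". Section 6.2.7 does the same for the second study medication after 30 days: "Those randomized to DSO will switch to a placebo and those randomized to DMEK will continue on dexamethasone". The DETECT II dosing table in section 6.1.2 shows the same split.

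**Who knows the operation.** Section 6.3 says "The eye bank will also inform the surgeon of the study" participant's surgical allocation. Participants, the BSCVA refractionist and the reading-center graders are the ones listed as masked.

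**Who makes discretionary decisions.** Section 6.5.1 says: "The masked treating physician will be allowed to add or change any therapy deemed necessary, including surgery". Section 6.5 says the same, and section 6.1.2 has a similar sentence directly under the DETECT II dosing table. Section 8.1 has the treating physician perform the slit lamp examination.

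**The concern.** One masking statement is applied to two designs, and only one of them can support it. In DETECT I drug is crossed with surgery, so a surgeon can know the operation and still not know the drug. In DETECT II drug and surgery are the same assignment. Identical bottles cannot hide the drug from someone who already knows the operation.

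This matters because decisions by those clinicians reach an endpoint. Section 9.1 lists need for further surgery among the Aim 1 complications, section 9.4.3 counts any re-grafting as graft failure, and section 2.3.1 names a second operation as a risk of DSO. A clinician who knows that an eye's steroid bottle is inert after day 30, or that only DSO eyes receive ripasudil, may add treatment or re-operate on a different threshold in the two arms. A reader relying on the stated masking would give the DETECT II complication comparison more credit than it has earned.

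The same bundling affects interpretation. Section 4.1 states the purpose of DETECT II as a comparison of two surgical interventions, and section 9.1 states the hypothesis as DMEK against DSO. The arms also differ in ripasudil and in steroid exposure.

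**Working it through.** **The plan's own DETECT II figure, for completeness.** Section 9.2 gives 30 per group for at least 90% power at 0.13 logMAR, SD 0.147, two-sided alpha 0.05, 10% loss. The adjusted SD is 0.163 × √(1 − 0.428²) = 0.147. The evaluable number per group is 2 × (1.960 + 1.282)² × 0.147² / 0.13² = 26.9, so 27, and 27 / 0.90 = 30. Normal-theory power with 27 per group is 0.901. The figure reproduces and does not depend on masking.

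**Can the drug be named from the operation?** Inputs are the arms and totals in sections 1.1 and 4.1. Equal cell sizes in DETECT I are an assumption.

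| | DETECT I | DETECT II |
|---|---|---|
| Arms | UT-DSAEK or DMEK, each with ripasudil or placebo | DMEK with placebo; DSO with ripasudil |
| Planned per cell | 160 / 4 = 40 | 60 / 2 = 30 |
| Chance of naming the drug, given the operation | 40 / 80 = 50% | 30 / 30 = 100% |
| Steroid after day 30 | one schedule for all arms | active in DMEK, placebo in DSO |

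In DETECT I knowledge of the operation carries no information about the drug. In DETECT II it settles both the drug and the later steroid assignment.

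**Role by role in DETECT II.**

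- *Surgeon.* Told the operation by the eye bank (6.3). Masking to medication is impossible.
- *Imaging technician.* Stated not to be masked to surgery (4.1, 6.3). Masking to medication is impossible. The images are graded by masked readers, so no consequence for graded outcomes follows from this alone.
- *Treating physician.* Called masked in 6.1.2, 6.5 and 6.5.1. The protocol describes no separate physician kept unaware of the operation, does not list the treating physician among those masked to surgery, and has that physician examine the operated eye at the slit lamp (8.1). Unmasking is a strong inference, not a stated fact.
- *Participant, refractionist, central graders.* Stated to be masked. Nothing in the surgery–drug link contradicts this.

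**Route to an outcome.** The possible path runs from knowledge of the arm, to added treatment or re-operation (6.5, 6.5.1), to the complication endpoint (9.1, 9.4.3). Treatment given before month 12 could also affect the acuity that the refractionist then measures without bias.

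**The case against.** The strongest reply is that little turns on the sentence. Surgeons cannot be masked to the operation they perform, so some differential management is inherent in comparing operations. The primary outcome has a masked assessor. Section 4.1 already describes DETECT II as outcome-masked, without the placebo-controlled label, and names ripasudil as part of the DSO arm. The ripasudil question in Aim 2 is confined to UT-DSAEK and DMEK, so DETECT II claims no separate drug effect. All of this stands and limits the size of the point. It does not make the masking statement true for DETECT II.

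Three stronger readings are tempting, and the document does not support them:

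- *That the treating physician is certainly unmasked, so rescue decisions are open-label as a matter of record.* The protocol never says whether this person is the surgeon. If a site uses a separate physician kept unaware of the operation, the claim would be wrong there.
- *That knowledge of the arm would bias the adverse event comparison through judgments of relatedness.* Section 8.3.4 requires every event to be documented whatever its relationship, section 9.4.3 tabulates and compares all adverse events, and section 9.4.4 reports totals. No planned comparison is confined to related events.
- *That therapy changes go unrecorded.* Sections 6.5 and 6.5.1 already require them to be recorded and reported. Only a by-arm display is being asked for, and the SAP, which is not at hand, may already contain one.

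**Conclusion.** The point holds as a contradiction within the protocol. For all 60 DETECT II participants, the surgeon and the imaging technician cannot be masked to study medication, and the placebo cannot mask any physician or staff member who knows the operation. For these roles the conclusion follows from the text and needs no outside assumption. For the treating physician it rests on the inference that no separate physician, unaware of the operation, is in place.

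The consequence is confined to discretionary co-treatment and re-operation, and so to the DETECT II complication endpoint, with a possible indirect effect on 12-month BSCVA. Its size cannot be computed from the document. DETECT I, the sample size, the masked measurement of BSCVA and the central image grading are unaffected.

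Two wording faults go with it. The synopsis calls DETECT II placebo-controlled although no DSO-plus-placebo arm exists, and section 4.1 does not use the term. Several statements of purpose and hypothesis name surgery alone where the contrast is DMEK against DSO with ripasudil and its own steroid regimen.

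**What to change.** - Limit the medication-masking statements in sections 4.1, 4.3 and 6.3 to DETECT I.
- For DETECT II, state that participants, the refractionist and the central graders are masked, and that the surgeon and imaging technician are masked to neither surgery nor medication.
- Say who the treating physician is in DETECT II. Drop the word masked in sections 6.1.2, 6.5 and 6.5.1 for that trial unless the person is truly kept unaware of the operation; if so, say how.
- Tabulate by arm the therapy changes and re-operations already recorded under sections 6.5 and 6.5.1, and interpret them as decisions by clinicians who may know the arm.
- Remove the placebo-controlled label from the DETECT II synopsis so that it agrees with section 4.1.
- State the DETECT II hypothesis and conclusion as DMEK versus DSO with ripasudil, noting the different steroid regimen, not as surgery alone.

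None of this changes a dose, a schedule or a clinical rule. The work is wording plus one table from data already collected. The cost is a less favourable masking claim for DETECT II.
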